8.5 Concomitant Medications

Individuals who have taken any medication other than paracetamol (acetaminophen) or oral contraceptives within 2 weeks prior to the imaging visit are excluded from the study. Subjects will receive thyroid blocking agent according to local practice before and after administration of DaTSCAN™ ioflupane (^{123}I) injection (Section 8.1.5).

Any medications taken by the subject from screening to the end of follow-up visit will be recorded in the CRF along with the indication and dosage. Either the generic or the trade name may be recorded. The sponsor/CRO will encode all therapy and medication according to a current well-recognised dictionary of medical codes.

8.6 Treatment Compliance

The IMP will be administered by study personnel. Each administration volume and the total radioactivity injected will be checked and the vial code, dose, and volume per administration will be recorded in each subject's CRF. A dose administered outside of specific dose requirements or defined range must be reported as protocol deviations (see Section 13.3).

9 STUDY PROCEDURES

All measurements obtained during the course of the study are summarised in the Study Schedule of Events ([Table 1](#)).

Table 1 Study Schedule of Events

Table 1 Study Schedule of Events

| Variables | Screening Visit (≤20 days before IMP) | Imaging Visit | | | | | | | | | | | | | | | Follow-up Visit (2 weeks ±2 days) |
|-----------|---|---------------------------|-------------------|-----|--------------------------|-------------------|--------------------|--------------------|--------------------|--------------------|------------------|------------------|------------------|------------------|------------------|------------------|-----------------------------------|
| | | Before IMP Administration | | IMP | After IMP Administration | | | | | | | | | | | | |
| | | Baseline | -1 h (±10 min) | | 0 | 5 min (±2 min) | 10 min (±5 min) | 15 min (±2 min) | 20 min (±5 min) | 30 min (±5 min) | 1 h (±10 min) | 2 h (±10 min) | 3 h (±10 min) | 4 h (±10 min) | 5 h (±10 min) | 6 h (±10 min) | 24 h (±2 h) |

AE = adverse event; ECG = electrocardiogram; h = hours; min = minutes; shaded areas indicate continuous measurement or monitoring

a Time point window is ±1 hour.

b Time point window is ±30 minutes.

c Time point window is ±10 minutes.

d Time point window is ±20 minutes.

e Time point window is ±5 minutes.

f The dosage and timing of administration will be based on investigator's discretion according to local practice of the study centre (Section 8.1.5).

9.1 Screening Visit

The screening visit must take place within 20 days before IMP injection. At the screening visit, demographic information and concomitant medications will be recorded; clinical laboratory tests, vital signs and oxygen saturation, and a complete medical and surgical history will be taken; and a physical examination, including 12-lead ECG, will be performed. For women of child-bearing potential, a serum beta-human chorionic gonadotropin (β -hCG) test for pregnancy will be performed.

To be eligible for this study, subjects must satisfy all entry criteria (fulfil all of the inclusion criteria listed in Section 7.2 and none of the exclusion criteria listed in Section 7.3). A signed and dated informed consent form must be obtained from all subjects prior to their entering the study.

Waivers or protocol exceptions will not be granted prospectively by the sponsor under any circumstances. Any exceptions to protocol-specified requirements will be considered to be protocol deviations.

AE will be monitored after signed and dated informed consent is obtained.

9.2 Imaging Visit

The imaging visit must start within 20 days after the screening visit. This visit will last approximately 48 hours.

9.2.1 Before IMP Administration

During the baseline period (defined as “after the screening visit up to 1 hour prior to administration”), the following will be recorded/conducted:

- Confirm inclusion/exclusion criteria
- Concomitant medications recording
- Physical examination and injection site monitoring
- Vital signs and oxygen saturation
- Thyroid blocking (see Section 8.1.5)
- Urine β -hCG test for pregnancy (for women of child-bearing potential)
- AE monitoring

Subjects will avoid all food and drink (except water) for 2 hours before and 2.5 hours after injection of DaTSCAN™. Then, light meals and unlimited decaffeinated/noncarbonated drinks are permitted out to 6 hours after injection. After that, there are no food restrictions, but caffeinated/carbonated drinks are limited to 4 cups per 24-hour period.

For subject comfort and prior to IMP administration, subjects will be advised to empty their bladder, and if necessary, have a bowel movement prior to positioning on the scanner and the initial scan commencing.

For women of child-bearing potential, the urine β -hCG test for pregnancy will be performed. These subjects cannot participate in the study until the result of the urine β -hCG test is found to be negative.

At approximately 1 hour before injection of IMP, 12-lead ECG, and vital signs and oxygen saturation will be recorded, and a tolerability questionnaire filled out. Collection of urine will begin. A blood sample for biodistribution and radiation dosimetry will be collected. Two cannulas (or indwelling catheters) will be placed, one is in left/right arm/antecubital vein for blood sampling, the other is in contralateral side for IMP administration. The injection site will be examined for any abnormal findings prior to IMP administration.

9.2.2 IMP Administration

The IMP will be administered by bolus IV injection, injected slowly (15 to 20 seconds) into an arm vein under aseptic technique, contralaterally to the sampling catheter.

9.2.3 After IMP Administration

The following will be performed after IMP administration:

- 12-lead ECG will be performed at 2 hours (\pm 30 minutes) and 5 hours (\pm 30 minutes) after IMP administration.
- Blood (up to 5 mL) samples for biodistribution and radiation dosimetry will be collected at 5 minutes (\pm 2 minutes), 15 minutes (\pm 2 minutes), and 30 minutes (\pm 5 minutes) and at 1 hour (\pm 10 minutes), 2 hours (\pm 10 minutes), 3 hours (\pm 10 minutes), 4 hours (\pm 10 minutes), 5 hours (\pm 10 minutes), 24 hours (\pm 2 hours), and 48 hours (\pm 3 hours) after IMP administration.
- Each urine excreted from approximately 1 hour before ioflupane (^{123}I) injection to 48 hours after ioflupane (^{123}I) injection will be collected as voided.
- Subjects will undergo simultaneous whole body (head to mid-thigh) anterior and posterior planar scintigraphy scans at 10 minutes (+ 10 minutes), 1 hour (\pm 10 minutes), 2 hours (\pm 10 minutes), 4 hours (\pm 20 minutes), 5 hours (\pm 20 minutes), 24 hours (\pm 2 hours), and 48 hours (\pm 3 hours) after IMP administration. A reference source will be imaged alongside the subject.

- Brain SPECT imaging will be performed at 3 hours (\pm 10 minutes) and 6 hours (\pm 10 minutes) after IMP administration.
- Physical examination and injection site monitoring will be performed at 4 hours (\pm 30 minutes) after IMP administration.
- Clinical laboratory test (blood and urine) samples will be obtained at 3 hours (\pm 1 hour) and 48 hours (\pm 3 hours) after IMP administration.
- Vital signs and oxygen saturation will be recorded at 10 minutes (\pm 5 minutes), 20 minutes (\pm 5 minutes), and 30 minutes (\pm 5 minutes) and at 1 hour (\pm 10 minutes), 2 hours (\pm 10 minutes), 4 hours (\pm 10 minutes), 24 hours (\pm 2 hours), and 48 hours (\pm 3 hours) hours after IMP administration.
- A tolerability questionnaire will be completed at 15 minutes (\pm 5 minutes) and 1 hour (\pm 10 minutes), 4 hour (\pm 10 minutes), 24 hours (\pm 2 hours), and 48 hours (\pm 3 hours) after IMP administration.
- Thyroid blocking (see Section [8.1.5](#))
- AE monitoring.
- Concomitant medications recording

See Study Schedule of Events ([Table 1](#)) for further details. Full details of the image protocol are presented in the GE-001-023 Imaging Manual.

9.3 Follow-up Visit

The follow-up visit will be conducted 2 weeks (\pm 2 days) after IMP administration. The following will be performed during this visit:

- Concomitant medications recording
- Physical examination
- Vital signs and oxygen saturation
- Clinical laboratory test (blood and urine)
- Urine β -hCG test for pregnancy (for women of child-bearing potential)
- AE monitoring

10 OUTCOME MEASURES

10.1 Primary Outcome Measures (Safety Variables)

The primary objective of this study is to evaluate the safety of a single dose of ioflupane (^{123}I) injection in Chinese HVs.

Safety variables will include monitoring of the following:

- Occurrence of AEs up to study exit
- Results of a tolerability questionnaire to be completed at prespecified time points
- Results of physical examinations at prespecified time points
- Results of clinical laboratory tests at prespecified time points
- Results of injection site monitoring at prespecified time points
- Results of vital signs (blood pressure, heart rate, body temperature, respiratory rate) and oxygen saturation at prespecified time points
- Results of ECG examinations at prespecified time points

Prespecified normal limits for vital signs, oxygen saturation and ECG intervals are provided in Section 15.3.

10.1.1 Clinical Laboratory Evaluation

Clinical laboratory parameters assessed in this study are displayed in [Table 2](#).

Table 2 Clinical Laboratory Parameters

| Serum Biochemistry | Haematology | Urinalysis |
|---|--|-------------------|
| Alanine aminotransferase (ALAT) | C-reactive protein | Bilirubin |
| Albumin | Haematocrit | Glucose |
| Alkaline phosphatase | Haemoglobin | Ketone |
| Amylase | Red blood cell count | Occult blood |
| Aspartate aminotransferase (ASAT) | White blood cell count | pH |
| Bicarbonate | Platelet count | Protein |
| Bilirubin (total, direct, indirect) | Prothrombin time (PT) | Specific gravity |
| Calcium | Activated partial thromboplastin time (APTT) | Urobilinogen |
| Chloride | Thrombin time (TT) | |
| Creatine phosphokinase (total) (CPK) | Fibrinogen (FIB) | |
| Creatinine | | |
| Gamma-glutamyltransferase (G-GT) | | |
| Glucose | | |
| Lactate dehydrogenase | | |
| Phosphorous | | |
| Potassium | | |
| Protein (total) | | |
| Sodium | | |
| Urea nitrogen | | |
| Uric acid | | |
| Thyroid function (at screening and 48 hours after IMP administration) | | |

The signed and interpreted laboratory results will be kept together with the subject's CRF as supplemental pages, both centrally and at the site.

All blood samples will be processed and handled per standard laboratory procedures. All retained samples will be destroyed according to local practice at site.

Urine will be collected from approximately 1 hour before IMP administration to 48 hours after IMP administration, as described in [Table 1](#). The time of void will be documented on the CRF. Urinalysis will be performed as described in [Table 2](#). Urine voided will also be analysed for radioactivity.

Any abnormal laboratory findings that constitute an AE (e.g., any abnormal findings leading to an intervention other than repeating the laboratory test) should be reported as such and should be followed up until the outcome is known.

Additional diagnostic tests may be indicated to determine a more precise diagnosis of the subject's condition (e.g., ordering a white blood cell [WBC] differential to help characterise a high or low WBC count, or ordering a determination of red cell indices to help characterise a low haematocrit).

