6 STUDY DESIGN

6.1 Overall Study Design and Plan

This is a phase 1, single-centre, single-group, nonrandomised, noncomparative, open-label, single-dose study to evaluate the safety, biodistribution, internal radiation dosimetry, and ED of DaTSCAN™ ioflupane (^{123}I) injection in Chinese HVs. Eight evaluable subjects (4 males and 4 females) will be included in the study. The study will be conducted at a single centre in the People's Republic of China.

The study will consist of a minimum of 3 visits for each subject. Each subject will attend a screening visit within 20 days before injection, an imaging visit, and a follow-up visit approximately 2 weeks after injection. During the screening visit, the subjects must satisfy all entry criteria and undergo safety assessments.

During the imaging visit, each subject will receive, by bolus IV administration, a single dose of ioflupane (^{123}I) injection with a nominal iodine (^{123}I) activity of $111\text{ MBq} \pm 10\%$ and will undergo simultaneous whole-body (head to mid-thigh) anterior and posterior planar scintigraphy scans at 10 minutes, 1 hour, 2 hours, 4 hours, 5 hours, 24 hours, and 48 hours after administration. Brain SPECT imaging will be performed at 3 and 6 hours after administration. A reference source will be imaged alongside the subject. Time-activity curves will then be generated from ^{123}I activity data from all 8 subjects and integrated to obtain the normalised-cumulated activity in each source region, which will then be used along with the Medical Internal Radiation Dosimetry (MIRD) schema to determine the internal radiation dosimetry. The dosimetry will be evaluated for the Cristy-Eckerman female and hermaphrodite male phantoms.

For evaluation of the biodistribution and radiation dosimetry, blood (up to 5 mL) samples will be collected at 1 hour before administration of ioflupane (^{123}I) injection and at the following times after administration of IMP: 5, 15, 30 minutes and 1, 2, 3, 4, 5, 24, and 48 hours. Urine excreted from 1 hour before administration of ioflupane (^{123}I) injection to 48 hours after administration will be collected as voided.

At the follow-up visit, all subjects will undergo specified safety assessments, and all female subjects of childbearing potential will also have a urine pregnancy test.

[figure not shown]
All subjects' safety will be monitored during the course of the study. The safety analysis will include the following:

- AEs up to study exit.

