6.4 Risks and Benefits to Subjects

As is true for many phase 1 studies, there are no expected direct benefits to HVs who will be subjects in this trial. However, data collected from study participants may help others (especially patients) prospectively by contributing to a knowledge base for further evaluation of the use of DaTSCAN™ ioflupane (¹²³I) injection.

The risks to subjects mainly relate to the IV injection and the radiation emitted by the drug. From previous experience, IV injection is known to carry a small risk of infection and haematoma. This risk is not related to the IMP but to the procedure itself. IV lines will be placed and monitored by qualified personnel in order to minimise risk to the subjects.

DaTSCAN™ is a radiopharmaceutical. As such, it exposes the recipient to ionising radiation. However, previous studies have shown that the effective radiation dose is 21 to 24 μ Sv/MBq, so the dose for this procedure is approximately 2.7 mSv, which is slightly over the published annual ED equivalent from natural radiation in China [Ziquiang et al 1994]. As the product is a radiopharmaceutical intended for diagnostic use, evaluation of dosimetry estimates is

mandatory for a marketing authorisation. Therefore, administration of a radioactive dose is unavoidable. However, the dose chosen for this study is based on previous experience to ensure that useful images can be obtained while minimising the radiation exposure to the HV. Administration of a radioactive dose that would not yield useful evaluable images would be unethical.

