8.1.4 Comparator

No comparator is to be used in this study.

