10.1.7 Adverse Events

All AEs/SAEs that occur after informed consent shall be recorded in the AE/SAE report form (see the Study Schedule of Events, [Table 1](#)).

Study personnel must remain vigilant for the occurrence of AEs, particularly those that may be life threatening. Personnel who are trained in the acute management of anaphylaxis and other emergencies and who have access to appropriate clinical supplies must be immediately available for no less than 60 minutes to observe for possible anaphylactoid reactions after dosing. Treatment of SAEs should be primarily supportive of vital functions.

An AE is defined as any untoward medical occurrence in a patient or clinical investigation subject which does not necessarily have to have a causal relationship with the IMP. AEs will be asked for from time of informed consent through the follow up visit at 2 weeks (\pm 2 days) after IMP administration.

A treatment-emergent AE (TEAE) is any unfavourable and unintended sign, symptom, or disease temporally associated with the use of DaTSCAN™, whether or not considered related to that product. Only symptoms/signs that begin or worsen in severity and/or frequency after DaTSCAN™-administration/use will be recorded as TEAEs in the CRF.

The subjects will be closely observed and questioned for any kind of AE during the study procedures and at follow-up appointments throughout the study period with non-leading questioning (e.g., “How do you feel?”). The subjects will be instructed to immediately report any symptoms and signs to the study staff.

Both the investigator(s) and sponsor/CRO will perform a causality assessment on any AE, to assess whether or not there is a reasonable possibility (evidence to suggest) that the IMP caused the event.

Causal relationship

Both the investigator(s) and sponsor/CRO will perform a causality assessment on any AE, to assess whether or not there is a reasonable possibility (evidence to suggest) that the IMP caused the event.

The relationship of an AE with DaTSCAN™ will be assessed and reported by the investigator as:

- Reasonably related to study drug (“Reasonable cause”): - A causal relationship between DaTSCAN™ and an AE is at least a reasonable possibility, i.e., the relationship cannot be ruled out.
- Not reasonably related to study drug (“Not reasonable cause”): - A causal relationship between DaTSCAN™ and an AE is not a reasonable possibility.

Expectedness

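### Thyroid function at 48 h, AE causality and the injection-site scores cannot separate DaTSCAN from thyroid blocking and cannulation, which every subject also receives; three inexpensive changes would help

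*Combined protocol and SAP*

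**What the plan says.** The study is a "single-group, nonrandomised, noncomparative, open-label, single-dose study" (6.1), and 8.1.4 adds "No comparator is to be used in this study". On size, 6.1 states "Eight evaluable subjects (4 males and 4 females) will be included in the study". The primary objective is safety (section 5).

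**Thyroid function.** Section 8.1.5 makes thyroid blocking mandatory before and after the injection. It gives, as an example, 1 to 4 h before and 12 to 24 h after; a note to Table 1 leaves dose and timing to the investigator. The Table 2 entry is "Thyroid function (at screening and 48 hours after IMP administration". Screening, up to 20 days before dosing, is the laboratory baseline (6.1, 6.2.2). Section 9.3 schedules "Clinical laboratory test (blood and urine" at 2 weeks, but by Table 2 thyroid function is not part of it. Section 12.5.1 tabulates changes above 40% and 80% of the normal span, and shift tables.

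**AE causality.** Section 10.1.7 reads "The relationship of an AE with DaTSCAN™ will be assessed and reported by the investigator as", followed by two grades, both about DaTSCAN. The related grade covers any case where a relationship cannot be excluded. Section 10.1.5 records every abnormal injection-site finding as an AE. On infection and haematoma from IV injection, 6.4 says "This risk is not related to the IMP but to the procedure itself". Section 12.5.5 summarises by relationship to the IMP only.

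**Site scores.** In 9.2.1 the paragraph on the -1 h assessments names the questionnaire first and only later says "Two cannulas (or indwelling catheters) will be placed, one is in left/right arm/antecubital vein for blood sampling", with the other cannula on the opposite side for the injection. Three of the five VAS items in 10.1.6 concern the injection site: pain, itch and loss of function.

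**The concern.** With no comparator, a safety finding can be attributed to DaTSCAN in two ways: by comparison with a suitable pre-dose value, or by the investigator's causality grade. Section 6.2.2 relies on both when it calls the safety analyses adequate to assess the effects of giving ioflupane. For the three measures here, one of these routes is incomplete.

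Three things are at stake. A thyroid shift in the 48 h tables could be read as a DaTSCAN effect, with no scheduled test to show whether it resolved. A haematoma from a cannula, or a reaction to the blocker, has no field in which its suspected cause can be recorded. Discomfort from the cannula could appear in the pre-to-post boxplots (12.5.6) as discomfort from the injection.

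**Working it through.** The plan gives no sample size calculation, power or event rate for safety (12.8, 12.9), so there is no stated figure to reproduce. The check is which effects each before/after comparison can estimate.

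**1. Thyroid function.** Let a reading be m + D + B + P, where m is the pre-treatment level and D, B and P are the effects of DaTSCAN, blocker and procedure.
- Screening: (m, D, B, P) = (1, 0, 0, 0)
- 48 h: (1, 1, 1, 1)
- Difference: D + B + P

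The eight subjects repeat the same two rows, so the design has rank 2 for 4 parameters. The sum is estimable; D alone is not. On the example timing both blocker doses fall between the two readings. A 2-week value also follows both agents, so it would show recovery but not separate them.

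**2. Site scores.** Assume the first blocker dose has been taken by -1 h, so that it cancels.
- Questionnaire before the cannula: pre (1, 0, 1, 0), post (1, 1, 1, 1), difference D + P. D is not estimable.
- Questionnaire after the cannula: pre (1, 0, 1, 1), post (1, 1, 1, 1), difference D. This takes the cannula effect as constant over time.

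Which case applies depends on an order that 9.2.1 does not fix.

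**3. AE causality.** One event graded as related is 1/8 = 12.5%, against 0/8 = 0%. The exact 95% limits are 0 to 36.9% for 0/8 and 0.3% to 52.7% for 1/8.

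The documents give no rate for AEs caused by the blocker or procedure. For an assumed per-subject risk p, the chance of at least one among 8 subjects is 1 - (1 - p)^8:

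| Assumed p | Chance of at least one in 8 |
|---|---|
| 5% | 0.34 |
| 10% | 0.57 |
| 20% | 0.83 |
| 30% | 0.94 |

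These are chances that such an event occurs, not that it is graded as related to DaTSCAN.

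**The case against.** A reader might infer that the primary safety results as a whole are confounded. The documents do not support that. Vital signs, oxygen saturation and ECG have a -1 h value, and 12.1 takes the last pre-dose observation as baseline. The site scores also have a -1 h value, and 9.2.1 has the injection site examined before dosing. All safety analysis is descriptive, with no confirmatory test (12.5).

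A reader might also infer that the plan reports blocker and cannula effects as DaTSCAN effects. It does not prescribe that. A TEAE is defined by timing, whether or not it is related. A not-related grade is available, the sponsor or CRO assesses causality as well as the investigator, and the time and dose of the blocker are recorded (8.1.5). What remains is that a not-related grade does not say what the cause was, and no field links an AE to the blocker or the procedure. The CRF and Safety Management Plan are not in the documents and could contain more.

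On the questionnaire, the order in 9.2.1 may not be chronological: the same paragraph also mentions the pre-dose blood sample before the sampling cannula. The body of Table 1 cannot be read in the available text. The order is therefore unstated, not prescribed wrongly. The objection stands to that extent, and it is also why one clarifying sentence is enough.

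On thyroid function, 10.1.1 already requires follow-up of an abnormal result that constitutes an AE. A shift below that threshold has no scheduled repeat.

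Finally, the 12.5% is arithmetic on a hypothetical event, and the limits for 0/8 and 1/8 overlap heavily. That is accepted: it shows how much one classification counts at n = 8, not what will happen.

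**Conclusion.** The point holds for three measures and no further.

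(a) The 48 h thyroid change estimates the combined effect of DaTSCAN, blocking and procedure in all 8 subjects and cannot be assigned to DaTSCAN. That both blocker doses fall in the interval rests on the example timing in 8.1.5. Follow-up is not scheduled unless the result constitutes an AE.

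(b) AE causality has no place for the blocker or the procedure, although 6.4 attributes two named risks to the procedure. One event graded as related changes the rate by 12.5 percentage points.

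(c) Three of the five questionnaire items may have a pre-dose value without the cannula component, if 9.2.1 is followed in the order listed.

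This limits interpretation in a study that is single-arm by intent. It is not an arithmetic error or a contradiction, and it does not undermine the other safety measures. The changes are worth making because they are cheap and safety is the primary objective.

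**What to change.** 1. State in 9.2.1 that the -1 h questionnaire is completed after the injection-arm cannula is in place. Cost: one sentence.
2. Add thyroid function to the 2-week draw, to show recovery and not to separate the agents. In 12.5.1, label the 48 h change as following DaTSCAN plus thyroid blocking. Cost: eight assays on a draw already scheduled, and a table label.
3. Add one CRF item per AE for relationship to the thyroid blocker or to cannulation/sampling, and tabulate it beside the DaTSCAN relationship in 12.5.5. Cost: one field and one extra judgement per AE.

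None of these needs a new visit or needle, or changes dosing or the blocking regimen.

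Scoring the sampling arm as a within-subject control is tempting but not recommended. That arm has ten post-dose draws over 48 h (9.2.3), against a single 15 to 20 second injection in the other arm (9.2.2). Subtracting its scores would also remove discomfort from repeated sampling and could mask a real DaTSCAN effect at the injection site.
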